# **3. ENDPOINTS AND BASELINE VARIABLES: DEFINITIONS AND CONVENTIONS**

#### **3.1. Primary Endpoints**

#### 3.1.1. Primary Safety Endpoints

- Prompted local reactions (redness, swelling, and pain at the injection site) within 7 days after each dose
- Prompted systemic events (fever, decreased appetite, drowsiness/increased sleep, and irritability) within 7 days after each dose
- AEs from Dose 1 through 1 month after Dose 3 and from Dose 4 through 1 month after Dose 4
- SAEs during the study (from Dose 1 through 6 months after Dose 4)
- NDCMCs during the study (from Dose 1 through 6 months after Dose 4)

## 3.1.1.1. Local Reactions

The local reactions assessed and reported in the e-diary are redness, swelling, and pain at the 20vPnC or 13vPnC injection site, from Day 1 through Day 7 after each dose, where Day 1 is the day of each dose.

CCI			
	PFIZER CONFIDENT	IAL	

Page 7

#### Severity and Maximum Severity

Redness and swelling will be measured and recorded in measuring device (caliper) units (range: 1 to >14; an entry in the e-diary of 15 will denote >14), and then categorized during analysis as mild, moderate, or severe based on the grading scale in Table 4. Grade 4 will not be collected in the e-diary but will be collected as an AE on the CRF. Measuring device units can be converted to centimeters according to the following scale: 1 measuring device unit = 0.5 cm. Pain at the vaccine injection site will be assessed by the participant's parent(s)/legal guardian(s) as mild, moderate, or severe according to the grading scale in Table 4.

Table 4. Graving Scales for Elocar Reactions					
Local Reaction	GRADE 1	GRADE 2	GRADE 3 a	GRADE 4 b	
	Mild	Moderate	Severe		
Redness	1 to 4 caliper units	5 to 14 caliper units	>14 caliper units	Necrosis or exfoliative	
	(or measuring device	(or measuring device	(or measuring device	dermatitis	
	units)	units)	units)		
	=	=	=		
	>0 to 2.0 cm	>2.0 to 7.0 cm	>7.0 cm		
Swelling	1 to 4 caliper units	5 to 14 caliper units	>14 caliper units	Necrosis	
	(or measuring device	(or measuring device	(or measuring device		
	units)	units)	units)		
	=	=	=		
	>0 to 2.0 cm	>2.0 to 7.0 cm	>7.0 cm		
Pain at injection site	Hurts if gently	Hurts if gently	Causes limitation of	Emergency room visit	
(tenderness)	touched	touched, with crying	limb movement	or hospitalization for	
	(eg, whimpers,			severe pain (tenderness)	
	winces, protests, or			at injection site	
	withdraws)				

 Table 4.
 Grading Scales for Local Reactions

Abbreviation: CRF = case report form.

Note: If the size of the redness and/or swelling falls between 2 measuring device units, the higher measuring device unit number will be recorded in the e-diary.

- a. Parents/legal guardians of the participants experiencing local reactions >14 caliper units (>7.0 cm) are to be contacted by the study site. An unscheduled visit may be required.
- b. Grade 4 assessment should be made by the investigator. Grade 4 will not be collected in the e-diary but will be collected as an AE on the CRF.

For each local reaction after each dose, the maximum severity grade will be derived for the e-diary collection period (Day 1 through Day 7, where Day 1 is the day of each dose) as follows:

maximum severity grade = highest grade (maximum severity) within 7 days after vaccination (Day 1 through Day 7) among severity grades reported for that local reaction in the e-diary.

#### 3.1.1.2. Systemic Events (Systemic Event Symptoms and Fever)

The systemic events assessed and recorded in the e-diary are fever, decreased appetite, drowsiness/increased sleep, and irritability from Day 1 through Day 7, where Day 1 is the day of each dose.

Maximum temperature range over the period from Day 1 through Day 7 will be mapped into the ranges described in Table 6 for summary of maximum temperature.

The systemic events of decreased appetite, irritability, and drowsiness/increased sleep will be assessed by participants' parents/legal guardians as mild, moderate, or severe according to the grading scale in Table 5. Grade 4 will not be collected in the e-diary but will be collected as an AE on the CRF.

Systemic Event	Mild	Moderate	Severe	
	Grade 1	Grade 2	Grade 3	Grade 4 a
Decreased appetite	Decreased interest	Decreased oral	Refusal to feed	Emergency room visit or
(loss of appetite)	in eating	intake		hospitalization for severe
				decreased appetite (loss of
				appetite)
Drowsiness	Increased or	Slightly subdued,	Disabling, not	Emergency room visit or
(increased sleep)	prolonged	interfering with	interested in usual	hospitalization for severe
	sleeping bouts	daily activity	daily activity	drowsiness (increased sleep)

#### Table 5. Grading Scales for Systemic Events

Systemic Event	Mild	Moderate	Severe	
	Grade 1	Grade 2	Grade 3	Grade 4 a
Irritability	Easily consolable	Requiring	Inconsolable;	Emergency room visit or
(fussiness)		increased attention	crying cannot be	hospitalization for severe
			comforted	irritability (fussiness)
(synonymous with				
restless sleep;				
decreased sleep)				

 Table 5.
 Grading Scales for Systemic Events

Abbreviation: CRF = case report form.

a. Grade 4 assessment should be made by the investigator. Grade 4 will not be collected in the e-diary but will be collected as an AE on the CRF.

Temperatures recorded in degrees Fahrenheit will be programmatically converted to degrees Celsius first for reporting. Fever will be grouped into ranges for the analysis according to Table 6.

#### Table 6.Ranges for Fever

≥38.0°C to 38.4°C	
>38.4°C to 38.9°C	
>38.9°C to 40.0°C	
>40.0°C	

Note: Fever is defined as temperature  $\geq 38.0^{\circ}$ C.

#### **3.1.1.4.** Adverse Events

AEs will be categorized according to MedDRA terms. AEs will be assessed from the time of informed consent through 1 month after Dose 3 and from Dose 4 through 1 month after Dose 4.

The primary endpoint "AEs from Dose 1 through 1 month after Dose 3" and "from Dose 4 through 1 month after Dose 4" and other supportive AE endpoints will be summarized by system organ class and preferred term on a participant level.

This primary endpoint will be supported by summaries and listings of related AEs, severe AEs, and immediate AEs (within the first 30 minutes after each dose).

AE reporting will be based on the specific reporting period. Missing AE start dates will be imputed following the Pfizer data standard rules as described in Section 5.3.

A 3-tier approach will be used to summarize AEs from Dose 1 through 1 month after Dose 3 and, separately, from Dose 4 through 1 month after Dose 4. Under this approach, AEs are classified into 1 of 3 tiers. Different analyses will be performed for different tiers (see Section 6.1.1.3.1).

- Tier 1 events: These are prespecified events of clinical importance and are identified in a list in the product's Safety Review Plan. No Tier 1 events have been identified to date for 20vPnC.
- Tier 2 events: These are events that are not Tier 1, but are "relatively common." A MedDRA preferred term is defined as a Tier 2 event if there are at least 1% of participants with the AE term in at least 1 vaccine group.
- Tier 3 events: These are events that are neither Tier 1 nor Tier 2.

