4.1.2. Approximate Number of Participants

Approximately 1500 participants will be randomized (approximately 1000 in the 20vPnC group and approximately 500 in the 13vPnC group).

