9.4.1. Safety Analyses

All safety analyses will be performed on the safety population.

Primary	• Descriptive statistics will be provided for each reactogenicity endpoint for each dose and vaccine group. Local reactions and systemic events from Day 1 through Day 7
	 after each dose will be presented by severity cumulatively across severity levels. Descriptive summary statistics will include counts and percentages of participants with the indicated endpoint and the associated Clopper-Pearson 95% confidence intervals (CIs). Between-group differences (20vPnC – 13vPnC) in percentage and 2-sided 95% CIs will be provided. The Miettinen and Nurminen method will be used to derive the 95% CI for the difference in percentages between vaccine groups. AEs will be categorized according to Medical Dictionary for Regulatory Activities (MedDRA) terms. A 3-tier approach will be used to summarize AEs. Under this approach AEs are classified into 1 of 3 tiers: (1) Tier 1 events are prespecified events o clinical importance and are identified in a list in the product's safety review plan; (2) Tier 2 events are those that are not Tier 1 but are considered "relatively common"; a MedDRA preferred term is defined as a Tier 2 event if there are at least 1% of participants in at least 1 vaccine group reporting the event; (3) Tier 3 events are those that are neither Tier 1 nor Tier 2 events. For both Tier 1 and Tier 2 events, the 95% CIs for the difference in percentage of participants reporting the events between the 20vPnC and 13vPnC groups will be calculated using the Miettinen and Nurminen method. In addition, for Tier 1 events, the asymptotic p-values will also be presented for the difference in percentage of participants reporting the events, based on the same test statistic and under the assumption that the test statistic is asymptotially normally distributed. There is no Tier 1 events for each vaccine group. SAEs will be categorized according to MedDRA terms. Counts, percentages, and the associated Clopper-Pearson 95% CIs of SAEs and NDCMCs from Dose 1 to 6 months after Dose 4 will be provided for each vaccine group.
Secondary	• There are no secondary endpoints in the study.

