## 4. ANALYSIS SETS (POPULATIONS FOR ANALYSIS)

Analysis populations are defined for the statistical analysis of safety results in the table below. Data for all participants will be assessed to determine if participants meet the criteria for inclusion in each analysis population prior to unblinding and releasing the database for analysis, and the classifications will be documented per standard operating procedures.

Population	Description
Enrolled	All participants who sign the ICD.
Randomized	All participants who are assigned a randomization number in the IRT system.
Safety	All participants who receive at least 1 dose of the investigational product with safety follow-up after any dose.
	Participants will be grouped according to the vaccine as administered in the safety analysis.
	Safety data after Dose 4 will be summarized for the subset of the safety population who also receive Dose 4 with safety follow-up after Dose 4.

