#### 5.2.1. Analyses for Binary Data

Descriptive statistics for categorical variables (eg, proportions) are the percentage (%), the numerator (n) and the denominator (N) used in the percentage calculation, and the 95% CI where applicable.

The exact 95% CI for binary endpoints for each group will be computed using the F distribution (Clopper-Pearson). The 95% CI for the between-group difference for binary endpoints will be calculated using the Miettinen and Nurminen method.

The 3-tier approach will be used to summarize AEs. For both Tier 1 (if any are identified during the study) and Tier 2 events, a 95% CI for the between-group difference in proportions will be calculated based on the Miettinen and Nurminen method. In addition, for Tier 1 events (if any), the asymptotic p-values will also be presented for the difference in proportions, based on the same test statistic and under the assumption that the test statistic is asymptotically normally distributed. For Tier 3 events, counts and percentages for each vaccine group will be provided.

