6.1.1.3. Adverse Events

- 6.1.1.3.1. Main Analysis
- Estimands: •

CCI

- The percentages of participants reporting AEs from Dose 1 through 1 month after • Dose 3 (Section 2.1).
- The percentages of participants reporting AEs from Dose 4 through 1 month after • Dose 4 (Section 2.1).

- Analysis set: Safety population (Section 4).
- Analysis time points: Dose 1 through 1 month after Dose 3, Dose 4 through 1 month after Dose 4.
- Analysis methodology: 3-Tiered approach as described in Section 5.2.1. •
- Intercurrent events and missing data: No missing values will be imputed except for partial AE start dates (Section 5.3).
- Reporting results: For all 3 tiers, the numerator (n) and the denominator (N) used in the • percentage calculation, the percentage (%), and the corresponding 2-sided 95% CI for participants reporting any AE, each system organ class, and each preferred term within system organ class will be presented by vaccine group.

In addition, for AEs classified as Tier 2 events, the differences in percentages (20vPnC - 13vPnC) and associated 2-sided 95% CIs will be provided.

Further, for Tier 1 events, if any are identified, the difference in percentages, the associated 2-sided 95% CI for the risk difference, and the asymptotic p-values will also be provided.

CCI

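### Does the either-group 1% rule for Tier 2 adverse events tilt the displayed differences towards 20vPnC under 2:1 allocation, enough to change the rule?

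*SAP*

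**What the plan says.** Protocol 9.4.1 and SAP 3.1.1.4 sort adverse event terms into three tiers. In the protocol a preferred term is "defined as a Tier 2 event if there are at least 1% of participants in at least 1 vaccine group" reporting it; the SAP's wording is equivalent: "defined as a Tier 2 event if there are at least 1% of participants with the AE term in at least 1 vaccine group". The tier decides what is shown:

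- Tier 2 terms get a between-group contrast. SAP 6.1.1.3.1 provides, "for AEs classified as Tier 2 events, the differences in percentages" and their 95% intervals by the Miettinen-Nurminen method.
- Tier 3 terms get no contrast. SAP 5.2.1: "For Tier 3 events, counts and percentages for each vaccine group will be provided".
- Tier 1 is empty so far: "No Tier 1 events have been identified to date for 20vPnC". In practice Tier 2 is the only visible route to a contrast by preferred term.

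SAP 6.1.1.3.1 also requires, for all three tiers, n, N, the percentage "and the corresponding 2-sided 95% CI for participants reporting any AE, each system organ class, and each preferred term within system organ class", by vaccine group.

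Planned sizes are "approximately 1000 in the 20vPnC group and approximately 500 in the 13vPnC group" (Protocol 4.1.2). The rule is applied separately after Dose 4, in a smaller set: "Safety data after Dose 4 will be summarized for the subset of the safety population who also receive Dose 4" and have follow-up after it (SAP 4). SAP 5.1 states that there is no formal hypothesis test and that everything is descriptive.

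**The concern.** A percentage threshold applied to either group is easier to cross by chance in the smaller group. At the planned sizes a term qualifies with 5 cases on 13vPnC or 10 on 20vPnC. When the true rates are equal and well below 1%, the terms that earn a displayed difference are therefore enriched for chance excesses on the comparator, and 20vPnC looks safer in those rows.

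Describing safety is the trial's primary objective, 13vPnC is the stated comparator (Protocol 4.2), and the planning rates in Protocol Table 4, 0.1% to 0.5%, lie where the effect is strongest. A selection rule that leans towards the investigational vaccine deserves a check, even in a descriptive study.

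**Working it through.** **Inputs.** Group sizes 1000 and 500 (Protocol 4.1.2); the 1% either-group rule (SAP 3.1.1.4); 2-sided 95% intervals (SAP 5.2). Equal true rates p are assumed. Table 4 covers 0.1% to 0.5%; higher rates are added to show the range.

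**The plan's own figures.** Table 4 is 1 - (1 - p)^n. For n = 1000 this gives 63.2, 86.5, 95.0, 98.2 and 99.3%; for n = 500 it gives 39.4, 63.2, 77.7, 86.5 and 91.8%. All ten cells reproduce.

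**Who qualifies.** Let X ~ Bin(1000, p) on 20vPnC and Y ~ Bin(500, p) on 13vPnC, independent. A term is Tier 2 if X ≥ 10 or Y ≥ 5. At p = 0.5%:

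- P(Y ≥ 5) = 10.8% and P(X ≥ 10) = 3.1%.
- P(Tier 2) = 1 - (1 - 0.108)(1 - 0.031) = 13.6%.

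Summing the exact joint distribution over Tier 2 outcomes gives the direction and the mean of X/1000 - Y/500:

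| True rate | Terms in Tier 2 | Lower on 20vPnC, of those | Higher on 20vPnC, of those | Mean difference (points) |
|---|---|---|---|---|
| 0.3% | 1.9% | 94% | 5% | -0.68 |
| 0.5% | 13.6% | 78% | 21% | -0.35 |
| 0.7% | 39.7% | 62% | 35% | -0.15 |
| 1.0% | 79.9% | 50% | 44% | -0.03 |
| 1.5% | 99.1% | 46% | 48% | -0.001 |

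At 750/750 the mean is 0, so unequal allocation is the cause. The tilt is largest where few terms are shown and almost absent where most are.

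**Sensitivity to size at p = 0.5%.** The planned sizes are approximate, and one infant can move a cut-off. At 1002/501 the cuts become 11 and 6: 5.5% qualify, mean -0.44. At 1001/500, 89% are lower on 20vPnC, mean -0.48. At 1000/501, 58% are lower, mean -0.21; by 0.7% that split is about even (48% lower, mean -0.06). For Dose 4 sets of assumed size, 950/475 gives -0.41 and 900/450 gives -0.28.

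**Intervals that exclude zero.** These are the rows most likely to mislead. With p̂ = (X + Y)/N and N = 1500, the score statistic at difference 0 is

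z = (X/1000 - Y/500) / √[p̂(1 - p̂)(1/1000 + 1/500) · N/(N - 1)].

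Each cell is the percentage of all terms shown with |z| > 1.96 by chance: favouring 20vPnC / against it / net (nets from unrounded values).

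| True rate | Interval for every term | Current rule | Pooled count ≥ 5 |
|---|---|---|---|
| 0.3% | 3.70 / 0.26 / 3.43 | 0.89 / 0.03 / 0.87 | 1.59 / 0.26 / 1.33 |
| 0.4% | 3.31 / 0.71 / 2.60 | 1.67 / 0.13 / 1.54 | 2.33 / 0.71 / 1.62 |
| 0.5% | 3.12 / 1.19 / 1.92 | 2.27 / 0.37 / 1.90 | 2.71 / 1.19 / 1.52 |
| 0.7% | 2.88 / 1.80 / 1.08 | 2.70 / 1.10 / 1.60 | 2.82 / 1.80 / 1.03 |
| 1.0% | 2.71 / 2.02 / 0.69 | 2.70 / 1.86 / 0.84 | 2.71 / 2.02 / 0.69 |

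With no selection at all, the interval in unequal groups already leans this way for rare events. At 0.5% and below the current rule adds nothing to that net lean and shows fewer chance exclusions in both directions. The ratio of the two directions does rise at 0.5%, from 3.12/1.19 = 2.6 to 2.27/0.37 = 6.2, but only because both counts fall and the smaller falls proportionally more. From 0.6% to 1.0% the rule does add to the net lean, by at most about 0.5 points.

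**What an alternative buys.** A trigger on the pooled count does not depend on which group is high. At a cut of 5 the mean displayed difference is 0 at every equal rate and size checked, and at 1000/500 no contrast now shown is lost, since the smallest qualifying total is 0 + 5. In return:

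- At 0.5%, terms with a difference rise from 13.6% to 86.9%; at 0.3%, from 1.9% to 46.8%.
- The threshold for calling a term fairly common drops to 5/1500 = 0.33%.
- Chance exclusions at 0.5% rise from 2.27 + 0.37 = 2.64% to 2.71 + 1.19 = 3.90% of terms.
- The net lean in exclusions grows at 0.4% and below. At 0.5% it falls at 1000/500 (1.90 to 1.52) but rises at 1002/501 (1.22 to 1.52), 1000/501 (1.08 to 1.54) and 900/450 (1.52 to 1.60).

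Other pooled cuts move the balance again. At 0.5%, a pooled 1% (15 of 1500) selects 1.0% of terms and a pooled count of 10 selects 22.3%.

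**The case for a change.** The best case for a change is that per-group intervals do not replace a contrast. At 8/1000 against 0/500 the Clopper-Pearson intervals overlap (0.35 to 1.57% and 0 to 0.74%), yet the Miettinen-Nurminen interval for the difference excludes zero (0.04 to 1.57 points). That excess on 20vPnC is Tier 3 and gets no difference, while 0 against 5 the other way does. With a true excess on 20vPnC of 0.6% against 0.1%, the term reaches Tier 2 8.3% of the time and its mirror image 18.4%; a pooled cut of 5 shows them 77.7% and 37.1% of the time. The edit would be one sentence in each document.

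Part of this stands: the asymmetry is real, its direction favours 20vPnC, and a difference interval carries information that two separate ones do not. But withheld contrasts run both ways: 0-2, 0-3, 0-4 and 1-4 all exclude zero in favour of 20vPnC and are also left out. For commoner events the order reverses: 1.5% against 0.5% is promoted 93.9% of the time when 20vPnC is high and 87.4% when 13vPnC is. And n and N are given for every term, so a reader who doubts a Tier 3 row can compute its interval.

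**Conclusion.** No change is needed. The either-group 1% rule does select chance excesses on 13vPnC somewhat more often when true rates are equal and well below 1%: at 1000/500 and 0.5%, 13.6% of terms qualify, 78% of those are lower on 20vPnC, and the mean difference is -0.35 points. The tilt is nearly gone at 1% and its size depends on the exact group sizes. It affects only which preferred terms carry a displayed difference. Overall AE, SAE, NDCMC and reactogenicity results do not pass through the tier.

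The rule limits contrasts to terms that reach a familiar threshold. A pooled trigger would replace one conventional cut-off with another, centring the mean at the price of many more rows, more chance exclusions and a mixed effect on their net direction. A sponsor could reasonably choose either.

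This rests on independent binomial counts, equal true rates for the tilt figures, and assumed sizes for the Dose 4 set. The documents do not say how many terms fall in the affected range. Parts of SAP 6.1.1.3 are blacked out, so the statement that contrasts are limited to Tiers 1 and 2 relies on the visible text.

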## 3.1.1.5. Serious Adverse Events and Newly Diagnosed Chronic Medical Conditions

SAEs and NDCMCs will be categorized according to MedDRA terms. NDCMCs and SAEs will be collected from the signing of the ICD through the end of the study.

## 3.2. Secondary Endpoints

Not applicable.

## **3.4. Baseline and Other Variables**

Measurements or samples collected prior to Dose 1 are considered the baseline data for the assessments.

## 3.4.1. Demographics and Medical History

The demographic variables are age at Dose 1 (in days), sex (male or female), race (black/African American, American Indian or Alaskan native, Asian, Native Hawaiian or other Pacific Islander, white, multiracial, and not reported), country/region, gestational age, ethnicity (Hispanic/Latino, non-Hispanic/non-Latino, not reported), and racial designation (Indian subcontinent Asian, Southeast Asian, Japanese, Korean, Chinese, African, African-Caribbean, Australian aboriginal, Torres Strait Islander, other). In cases where more than 1 category is selected for race, the participant would be counted under the category "multiracial" for analysis. Age at Dose 1 in days will be derived as (Dose 1 date – date of birth + 1).

For participants who were randomized but not vaccinated, the randomization date will be used in place of the date of Dose 1 for age calculation. If the randomization date is also missing, then the informed consent date will be used for age calculation.

Medical history will be categorized according to MedDRA.

## 3.4.3. Prior/Concomitant Vaccines and Concomitant Medications

The name, date of administration, and site of administration for all vaccinations given on the same day as investigational product administration (Visits 1, 2, 3, and 5) will be summarized. At Visit 1, information on prior vaccinations received by the participant will be summarized.

Concomitant medications will be recorded only if they were used to treat SAEs and NDCMCs. Concomitant and prior vaccines and concomitant medications will be coded using the WHO Drug Dictionary.

## 3.5. Safety Endpoints

Local reactions, systemic events, AEs, SAEs, and NDCMCs have been described above (Section 3.1.1) in the primary safety endpoints.

## 4. ANALYSIS SETS (POPULATIONS FOR ANALYSIS)

Analysis populations are defined for the statistical analysis of safety results in the table below. Data for all participants will be assessed to determine if participants meet the criteria for inclusion in each analysis population prior to unblinding and releasing the database for analysis, and the classifications will be documented per standard operating procedures.

Population	Description
Enrolled	All participants who sign the ICD.
Randomized	All participants who are assigned a randomization number in the IRT system.
Safety	All participants who receive at least 1 dose of the investigational product with safety follow-up after any dose.
	Participants will be grouped according to the vaccine as administered in the safety analysis.
	Safety data after Dose 4 will be summarized for the subset of the safety population who also receive Dose 4 with safety follow-up after Dose 4.

